4.3 Patient Participants (Nested Qualitative Study)

From the 240 patient participants recruited to the intervention arm of the main feasibility study, we will recruit a sub-sample of up to 40 patient participants (6-7 from each Cardiology Centre). Eligible patients will be those who are participating in the feasibility study and have not withdrawn from the study.

4.4 Cardiology Department Staff (Nested Qualitative Study)

Eligible NHS staff participants will be:

- Working, or have worked, in the cardiology department delivering care for people scheduled for coronary angioplasty or "angio query proceed".
- Have had direct involvement in the delivery of CONNECT and/or the feasibility study procedures.

4.5 Co-enrolment

Patient participants who have been recruited into other interventional studies that do not involve an educational intervention, or significantly alter the amount of health professional contact, or involve the administration of self-report questionnaires, are permitted to be included in this feasibility study. Sites should contact the Chief Investigator to discuss details prior to co-enrolment.

5. CONSENT PROCESS

5.1 Patient participants

The local PI at each participating Cardiology Department, (or a trained delegate e.g., specialist nurse or clinical research nurse), will be responsible for obtaining oral informed consent from each patient participant. For consent to be valid it must be voluntary, informed, specific, current, and given by a person with capacity at the time.

Eligible patients will be identified and first approached by the local PI, or delegate, and provided with introductory information about the study. This person will be a member of the patient's care team. Interested patients will then be asked for their permission to share their personal details (hospital number, address, telephone, email) with the clinical research team. If they agree they will be sent a study pack (Invitation letter, patient information sheet, oral informed consent form and baseline questionnaires) by post or email. Potential patient participants will then be telephoned 3-5 days later to discuss the study, during which time oral informed consent will be sought from willing participants. Eligible participants will be asked if they have had sufficient time to read and consider the information in the patient information sheet (PIS) and given an opportunity to ask questions. During the oral consent process, the participant will be able to refer to a blank copy of the oral informed consent form (sent in the study pack) to support their understanding. The person seeking informed consent will explain to the patient participant:

- That consent is sought for regulatory authorities, members of the research team and or representatives of the sponsor to have direct access to participant's medical records.
- That consent is sought to take part in a feasibility study of a PtDA and a nested qualitative interview study for those in the intervention arm

- That the feasibility study will evaluate whether a future trial of a PtDA 'CONNECT' is possible
 and whether it will work in the NHS and be acceptable to patients and health professionals
- That the PtDA 'CONNECT' will be allocated at random to Cardiology Departments so not all
 participants will get to use it.
- What the study procedures will involve for the participant.
- That participation is voluntary, and they may withdraw from the study at any time, and that their decision will not influence their treatment and care.
- The anticipated benefits and risks of taking part in the study.
- The requirement to feedback to the local PI should any instances of poor clinical practice or safeguarding issues become apparent.
- Those participants taking part in the feasibility study, or qualitative interview study (intervention arm only), will be entered into a prize draw or receive a voucher, respectively.

The consent form for the intervention arm will have two sections. The first addresses participation in the main feasibility study, and the second addresses participation in the qualitative study, which takes place some months later. Informed consent for both elements will be sought simultaneously, and ongoing willingness rechecked ahead of the qualitative interviews. Since the qualitative study is only for participants in the intervention arm, the consent form for the control arm will only have one section that addresses participation in the main feasibility study. If the patient participant wishes to proceed, the researcher will sign the oral consent form on their behalf. The patient participant will be asked if they would like to receive a copy of the signed document.

The oral informed consent process will take place ahead of any study procedures and conducted as per an agreed Standard Operating Procedure. Details of the informed consent process (Date and summary of discussion and consent process followed) will be recorded in the patient medical record and CONNECT Study Log (Patients Identification Log, Patients Screening Log, Patients Participant Enrolment and Withdrawal Log). Participants will have the right to withdraw from the study at any time.

The local PI, or delegate, will liaise with their Research and Development department to ensure that the completed informed consent form is archived in the local site file and is available to the Chief Investigator for review if required. To reduce administration burden for GPs we have adopted a pragmatic approach and have chosen not to inform them about patients in their care participating in the study. This is because participation in the study is not anticipated to influence the patient health condition and the current workload for GPs in primary care settings is significant.

5.2 Health professional/NHS staff participants

During site set up and training, Cardiology Department staff in the intervention arm will be informed that they will have the opportunity to participate in a qualitative interview once all recruited patient participants at their site have completed their pre-assessment consultation. The local PI, or delegate, will identify NHS staff involved in the patient pathway for planned "angio query proceed", coronary angioplasty, and/or the delivery of CONNECT study procedures at their site. All eligible participants will be emailed a study pack (invitation letter, PIS and oral informed consent form) and invited to email, or telephone, the Research Fellow leading the qualitative study if interested in participating. The Research Fellow will contact interested individuals and ensure that they have had sufficient time to read the PIS, ask questions and deliberate with others. The Research Fellow will explain to the NHS staff participant:

That consent is sought to take part in a nested qualitative interview study

- The requirement to feedback to the local PI of any instances of poor clinical practice, or safeguarding issues, should they become apparent.
- What the study procedures will involve for the participant.
- The anticipated benefits and risks of taking part in the study.
- That participation is voluntary and that they may withdraw from the study at any time.
- Those participants taking part in the qualitative interview study will not be reimbursed for any expenses.

If the NHS staff participant wishes to proceed, the Research Fellow will sign the oral consent form on their behalf and asked if they would like to receive a copy of the signed document. Participants will have the right to withdraw from the study at any time.

The oral informed consent process will take place ahead of any study procedures and conducted as per an agreed Standard Operating Procedure. Details of the informed consent process (Date and summary of discussion and consent process followed) will be recorded in an NHS Staff Participant Log by the Research Fellow and archived as per the Open University data management plan.

6.0 Recruitment, Screening and Randomisation

6.1 Recruitment and screening

Recruitment will take place at three levels: 1) Cardiology Departments/Clusters in England. Then within Cardiology Departments/Clusters 2) patient and 3) health professional/NHS staff participants will be recruited.

6.1.1 Cardiology Departments/Clusters

Recruitment of Cardiology Departments/Clusters will be done through the dissemination of an Expressions of Interest (EoI) document by the National Institute of Health Research Yorkshire and Humber Clinical Research Network to all NHS Trusts in England that provide cardiology services. Informal meetings will be scheduled to discuss site suitability against eligibility criteria. Signing of an agreement will constitute consent to participate. The list of participating Cardiology Departments will be available on the trial registration site.

6.1.2 Patient Participants (Feasibility Study)

Potentially eligible patient participants who are scheduled for planned "angio query proceed" or coronary angioplasty will be screened and approached by a local PI, or a delegated person. We have adopted a flexible approach to recruiting patient participants as the patient pathway for planned angio/coronary angioplasty varies across NHS Trusts in England and is subject to change at short notice as measures are introduced to reduce waiting lists. We envisage that patient participants will be identified by a member of the direct care team within three settings:

1. Planned catheter laboratory waiting lists - by a catheter laboratory scheduler, specialist nurse, cardiologist trainee or consultant.

The local PI, or delegate, will identify eligible patients from the waiting list and contact them by telephone. The study will be briefly introduced, identified as optional and not related to their treatment. Interested participants will be asked to give their permission to share their personal details (name, patient hospital number, contact number, home address or email) with a member of the Clinical Research Team. Participants must have a minimum of a 2-week lead in time before their pre-assessment consultation (See Figure 1). This should be feasible because average

waiting times for elective cardiology procedures in England are between 13 and 20 weeks and are predicted to increase²³.

2. Cardiology outpatient clinics at the point of referral for planned coronary angioplasty or "angio query proceed" – by a specialist nurse or cardiologist trainee or consultant.

Patients are typically referred for planned coronary angioplasty, or "angio query proceed" by their cardiologist at an outpatient consultation, (Face-to-face, telephone or video consultation). The local PI, or delegate, will screen and approach eligible patients during this clinic and the same recruitment process described for waiting list participants will be adopted.

3. Chest pain clinics at the point of referral for planned coronary angioplasty or "angio query proceed" – by a specialist nurse or cardiologist trainee or consultant

Patients are typically referred for planned coronary angioplasty, or "angio query proceed" by their cardiologist or specialist nurse at chest pain clinics (Face-to-face, telephone or video consultation). The local PI, or delegate, will screen and approach eligible patients during this clinic and the same recruitment process described for waiting list participants adopted.

We will liaise with cardiology teams at site set-up to establish which approaches are both feasible and preferred. For all three recruitment pathways a member of the direct care team will screen and approach eligible patient participants, document in the medical record and complete the Patient Identification Log. For potential participants who speak languages other than English, an interpreter would normally be booked as part of standard practice. This would be recorded on the Patient Identification Log. If a patient does not want to be contacted, no further communication will be made regarding the study

The contact details of patient participants who are potentially interested in participating in the research will be shared with a member of the Clinical Research Team who will immediately post/email the Study Pack (Invitation Letter, Patient Participant Information Sheet, Patient Consent Form, Baseline questionnaires). For interested participants who speak a language other than English, study documents will be provided in the patient's first language and the research nurse will arrange an interpreter to be present during the telephone call. If a patient participant does not answer the phone or respond to emails, two further attempts at contact over a one-week period will be made. If no response, there will be no further contact about the study

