7.2 PtDA CONNECT

CONNECT (COroNary angioplasty dECision Tool) is a digital Patient Decision Aid hosted on a university website. Like other PtDAs, CONNECT is an intervention designed to encourage patient involvement in health-related decision-making. CONNECT is not a medical device. It is an educational tool, that goes beyond simply providing information. It uses multimedia (images, diagrams, animations, audio) to inform patients about their treatment choices and the associated risks and benefits of each. Through interactive activities (i.e., questions about angina symptoms, what matters to them and their preferred treatment choice) CONNECT enables users to clarify and communicate their personal values in relation to each treatment option. CONNECT generates a personalised summary derived from self-report questionnaires that can be saved as a PDF file. The summary identifies self-reported angina symptom burden and the impact on daily life, personal values, treatment preferences, worries, concerns, and unanswered questions. This personalised summary can inform patient consultations and potentially act as a 'primer' for health professionals, alerting them to specific areas that the patient may wish to discuss. See appendix 1. for a detailed description of CONNECT using the template for intervention description and replication (TIDieR) checklist²⁰. CONNECT is accessible at the following link https://uoh-replication (TIDieR) checklist²⁰. CONNECT is accessible at the following link https://uoh-replication (TIDieR) checklist²⁰. connect.staging.ginger-root.co.uk/

Patient participants at the Cardiology Departments in the intervention arm will receive information about how to access CONNECT either as part of usual care correspondence from the hospital confirming their pre-assessment consultation and/or procedure date. The information about CONNECT and the weblink or QR code will be delivered on a paper or digital letter, email, or text message, depending on the usual approach adopted by the Cardiology Department. Or, if this approach does not align with the patient pathway of care, then a Clinical research nurse will send CONNECT access instructions 1-2 weeks after consent.

Participants will be invited to use CONNECT and save their personal summary before attending their usual-care pre-assessment clinic consultation. To standardise the delivery of CONNECT across Cardiology Departments, we will create training materials that will be delivered during site set up.

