8.2.3 Baseline

Participants will have received the baseline (T1) questionnaires in the study information pack. This will include instructions to complete them within 7 days of consenting to participate and return in the stamped-addressed envelope or via e-mail to the Research Fellow. The baseline (T1) questionnaires are the 10-item Decisional Conflict Scale²³ and the bespoke coronary angioplasty knowledge questionnaire. The Research Fellow will collate returned questionnaires to determine the following outcomes:

- Number of returned self-report questionnaires at baseline (T1).
- Item response rate (Number of valid responses on each questionnaire divided by total number of responses requested).
- Number of patients who had complete data for each questionnaire at baseline.

Participant answers and questionnaire scores will be input into a CRF by the Research Fellow.

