8.2.7 Medical record review

At the end of the study the clinical research nurse will review participants' medical records to extract and document their actual treatment/procedure received (i.e., medicines only, or coronary angiogram only, coronary angioplasty, or other (e.g. no intervention)) and medical record review for all-cause mortality, Major Adverse Cardiovascular Events (MACE), defined as acute myocardial infarction, death due to a cardiac or unknown cause, emergency revascularization, ventricular arrhythmia, or cardiogenic shock) and rates of hospital readmission, 30-days after hospital discharge.

i. Patient Questionnaires

Table 4 below shows the timepoints for the administration of measures.

Measures	Enrolment	Baseline (T1)	Post Pre- Assessment (T2)
Brief Health Literacy Screening Tool (Chew et al 2004) ²¹	Х		
eHealth Literacy Scale (Norman & Skinner 2006) ²²	Х		
Decisional Conflict Scale (O'Connor, A. 2010) ²³		X	X

Coronary Angioplasty Knowledge questionnaire. (Researcher Team generated)	Х	Х
Preparation for Decision-Making Scale (Bennett et al. 2010) ²⁴		Х
Perceived Involvement in Care Scale (Lerman et al. 1990) ²⁵		Х

Enrolment: After informed consent for study participation.

Baseline: Before using CONNECT at least 1 week before Pre-Assessment Clinic.

Post Pre-Assessment Clinic: After pre-assessment, but before coronary angio/angioplasty procedure.

The Brief Health Literacy Screening Tool is a 3-item measure designed to evaluate functional health literacy with responses recorded on a 5-point Likert scale²¹. The tool takes approximately one minute to complete, can be administered orally, performs well compared to other longer standard measures, and has been shown to have adequate validity and reliability when administered by nurses in clinic settings²⁷.

The eHealth Literacy Scale is an 8-item measure designed to evaluate peoples' knowledge, comfort, and perceived skills at accessing and using health related electronic health information with responses recorded on a 5-point Likert scale²². It is the most frequently used measure to evaluate e-literacy, has acceptable psychometric properties, but has a relatively narrow scope having been designed before the era of social media²⁸. Regardless, other comparable measures have 18-items, or more, making them impractical for use in NHS settings.

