#### 4.1.1.Stop go criteria

Details of the 'Stop'/'Change'/'Go' criteria derived from data collected in this feasibility study will determine progression to a future large-scale evaluation (c-RCT).

Below is a table of the revised progression Criteria for the CONNECT feasibility study. The criteria were agreed with the study advisory group (SAG) prior to starting recruitment. These criteria will be used to determine whether a full c-RCT would be feasible.

Progression Criteria	Green- Go	Amber- Maybe	Red- Stop	Proposed action if Amber targets are attained
Cluster recruitment targets : Number of Cardiac Centres recruited in the first 3 months of the study.	8	5-7	≤4	Review reasons for non-participation on EoI document and consider alternative strategies.

Progression Criteria	Green- Go	Amber- Maybe	Red- Stop	Proposed action if Amber targets are attained
Patient recruitment targets : Average number of patients recruited per month, per cluster.	3+	2	≤1	Review recruitment processes and reasons for non-consent. Consider alternative strategies.
Adherence targets: % of the patient sample who access CONNECT before pre-assessment clinic. *	60%+	25%- 60%	<25%	Review qualitative data for reasons for non-adherence. Consider strategies to improve CONNECT engagement. Consider developing a non-digital version of CONNECT if non-adherence is largely due to low digital literacy levels.
Retention targets : % of the patient sample who complete the study.	80%+	60%- 80%	<60%	Review attrition reasons and identify strategies to prevent before full c-RCT.
Willingness to be randomised: % of Cardiac Centres who responded to the EOI that are willing to be randomised in the future c-RCT.	80%	60%- 80%	<60%	Review reasons for non-participation on EoI document and consider alternative strategies and/or trial designs, such as delayed-intervention trial.
Anticipated Primary Outcome acceptability: Average % item completion of the Time Point 2 Decisional Conflict Scale questionnaire. †	80%+	60%- 80%	<60%	Review the outcome measures with PPI group and revise ahead of c-RCT.
Patient and Cardiology Health Professional acceptability of CONNECT and study procedures.	-	-	-	Review qualitative data on patient and cardiology health professional acceptability of CONNECT.

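### At the 2-week minimum lead-in, the fallback CONNECT link can go out on or after clinic day, and the patient would still count as non-adherent.

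*Protocol*

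**What the plan says.** Protocol 6.1.2 sets the minimum within the waiting-list identification step: "Participants must have a minimum of a 2-week lead in time before their pre-assessment consultation (See Figure 1". The two clinic-based recruitment routes follow the same process. The eligibility list in Protocol 4.2 does not repeat the requirement.

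The steps after identification are:

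- **Pack.** Contact details pass to the research team, "who will immediately post/email the Study Pack" (Protocol 6.1.2).
- **Consent call.** "Potential patient participants will then be telephoned 3-5 days later to discuss the study" (Protocol 5.1). If there is no answer, "two further attempts at contact over a one-week period will be made" (Protocol 6.1.2).
- **T1 baseline.** Patients are told to "complete them within 7 days of consenting to participate" (Protocol 8.2.3). The notes to Table 4, repeated in SAP 2.7.4, define baseline as "Before using CONNECT at least 1 week before Pre-Assessment Clinic".
- **CONNECT link.** It travels with the hospital's appointment correspondence. Where that does not suit the local pathway, "then a Clinical research nurse will send CONNECT access instructions 1-2 weeks after consent" (Protocol 7.2).

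The adherence progression criterion is the percentage "of the patient sample who access CONNECT before pre-assessment clinic" (SAP 4.1.1), with Go at 60% or more; Protocol Table 1 has 75% or more. SAP 3.2 takes adherence over intervention-arm participants and makes no exception for a link sent late or not at all.

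**The concern.** A patient may enter with 14 days to the clinic. Several intervals must then run in sequence, and two of them (7 days for T1, 7-14 days to the fallback link) are each a large part of the 14. If they do not fit, staff can follow every written instruction and still send CONNECT on or after the day of the clinic it is meant to precede.

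That patient cannot meet the criterion, yet remains in its denominator. The result would be read as unwillingness or inability to use the tool, when the cause was the timetable. The per-protocol set (SAP 3.3) consists of those who accessed CONNECT, so it cannot separate non-delivery from non-use. SAP 4.1.1 and 4.3 plan no sensitivity or additional analyses.

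A second, smaller issue concerns the baseline. The Decisional Conflict model in SAP 4.1 adjusts for the T1 score. A T1 completed after using CONNECT could occur only in the intervention arm, and adjusting for it could remove part of any effect. The outcomes listed in Protocol 8.2.3 and 8.2.4 include neither a T1 completion date nor a link-sent date, so neither problem could be seen from them afterwards.

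**Working it through.** The documents give no derivation of the 14 days, so the check adds up the protocol's own intervals under each possible start.

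**Inputs.** Pack sent on day 0, with postal time ignored (6.1.2); call at +3 to +5 days (5.1); retries add up to 7 days, taken as running from the first call (6.1.2); T1 due by consent + 7 (8.2.3); T1 in window by clinic − 7 (Table 4 notes); fallback link at consent + 7 to + 14 (7.2); clinic on day 14; intervention arm of 240 (4.3).

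**Formulas.** T1 due = consent + 7. Latest in-window T1 = 14 − 7 = day 7. Link = consent + 7 to consent + 14. Days left = 14 − link day.

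| Lead-in starts at | Consent | T1 due | Latest in-window T1 | Fallback link | Days left to clinic |
|---|---|---|---|---|---|
| Identification, first call answered | day 3-5 | day 10-12 | day 7 | day 10-19 | 4 to −5 |
| Identification, with retries | day 3-12 | day 10-19 | day 7 | day 10-26 | 4 to −12 |
| Consent | day 0 | day 7 | day 7 | day 7-14 | 7 to 0 |

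**Counted from identification.** Full use of the T1 allowance plus the one-week gap needs (3 to 5) + 7 + 7 = 17 to 19 days, or up to 12 + 7 + 7 = 26 with retries. To stay in window, T1 must be done within 7 − 5 = 2 to 7 − 3 = 4 days of consent, and with retries consent itself can fall after day 7. Protocol Table 3 places identification 1-2 weeks before consent. On that timing, consent falls on day 7-14 and the fallback link on day 14-28, which is on or after clinic day.

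**Counted from consent.** 7 + 7 = 14, so T1 fits with no slack. The link leaves 7 to 0 days for a tool that Appendix 1 says took users up to an hour and that they valued being able to revisit.

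**Letter route.** Protocol 7.2 and 8.2.4 give no interval from consent or from T1, so there is nothing to add up. The order of T1 and link is unspecified on this route.

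**Effect on the criterion (illustrative).** Observed access = uptake when sent in time × (1 − fraction late).

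- SAP criterion: take 62%, the uptake in the SAP's footnote to the adherence target. The 60% line is crossed when the late fraction exceeds 1 − 0.60/0.62 = 3.2%, or 7.7 of 240. With 8 late: 0.62 × 232/240 = 59.9%.
- Protocol Table 1: assume 80% uptake. The 75% line is reached at 1 − 0.75/0.80 = 6.25%, or 15 of 240.

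**The case against.** The strongest reply is that the clash depends on an assumed start. The lead-in sentence points to Figure 1, which is not in the readable text and may settle the matter. Counting from consent gives 7 + 7 = 14 exactly, which suggests that this was intended. Even from identification the fastest path fits: call on day 3, link on day 10, and T1 in window if done promptly. All of this stands. A reader might infer that the lead-in is simply shorter than the required steps; the documents support that only for some start events and some paths.

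Next, few patients may be near the minimum. Protocol 6.1.2 cites average waits of 13-20 weeks, and Table 3, although broken in the text, appears to put pre-assessment about two months after consent. This also stands, with limits: the cited waits are to the procedure and not to pre-assessment, waiting-list recruitment can reach a patient late in the wait, and Table 3 calls its times approximate.

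A reader might also infer that adherence would fall by as many points as the percentage of short-wait patients. That would need everyone else to access CONNECT. At 62% uptake, each 10% sent the link late costs 6.2 points, and the documents give no figure for the share.

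On the baseline, T1 goes out before consent, the nurse gives a reminder at the consent call, and the Table 4 notes require T1 before CONNECT use. Holding the link before T1 is done is not the same as using it. Bias is possible, but nothing in the documents allows it to be sized.

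Finally, an Amber result triggers a review of reasons for non-adherence, so a scheduling cause might surface. But that review draws on qualitative data from a sub-sample of up to 40 and would not count the patients who were sent the link late.

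**Conclusion.** The point holds at the 14-day minimum. On the fallback route, the written intervals either do not fit or leave no slack, depending on a start event that the readable text does not give. Counted from identification, the link can go out from 4 days before the clinic to 5 days after it (12 with retries). Counted from consent, it can go out from 7 days before the clinic to clinic day itself. On either reading, a patient whose link arrives too late counts against adherence.

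Three limits apply. The letter route is unspecified, not shown to fail. A late T1 does not make a patient non-adherent; only lack of access does. The number of patients affected is unknown and may be small. The case for acting is that a small number could matter: 8 late among 240 takes 62% to 59.9%. That figure assumes the uptake cited in the SAP and no access by the late group before the clinic.

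**What to change.** Reconcile Protocol 5.1, 6.1.2, 7.2, 8.2.3, Table 3 and the Table 4 notes as follows.

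1. State that the lead-in runs from consent, the reading under which T1 fits.
2. Replace the fallback timing with a window that closes before the clinic by a margin the sponsor sets, and check or prompt T1 completion before the link is sent. Making receipt of T1 a condition by day 7 would not work, because a T1 completed and posted on day 7 cannot have been received by then.
3. Record the link-sent date and the T1 completion date. Flag and count any T1 completed after CONNECT use; do not discard it. Since SAP 4.2 uses no missing-data method, discarding would drop patients from the adjusted model in the intervention arm only.
4. Keep the all-participant adherence rate for the progression criterion. Beside it, report the number not sent the link before the clinic and the access rate among those sent it in time.

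The cost is protocol wording, two date fields and one extra descriptive row. A few patients with a short wait after consent would become ineligible.
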